**b. Measurements and evaluations**

1. Visit 1: Informed consent process will be conducted at this visit. Assessments include uncorrected and best-corrected ETDRS visual acuity (UCVA / BCVA), manifest refraction, intraocular pressure (IOP), and slit lamp examination including dilated fundus exam, auto refractor keratometry, Lenstar, VERION™ Reference Unit, and corneal topography (Atlas). Both IOL power and astigmatism correction will be calculated using the surgeon's current standard of care as well as using the VERION™ Image Guided System: Digital Surgical Planning. Any testing that is part of the site's standard of care preoperative cataract surgery evaluation may be performed prior to the informed consent being signed provided these tests are conducted within 90 days of the surgery and notation of the date performed is entered onto the source document.

The first eye undergoing surgery will be randomized to either one of the two groups: Group A (surgeon standard of care) or B (VERION™ Image Guided System + ORA System with VerifEye or VerifEye +). The fellow eye will be assigned to the alternate group. Eyes will be randomized after all calculations have been completed. Prior to randomization, all measurements, IOL power and astigmatism correction calculations will be reviewed following the practice standard of care to determine subject's eligibility for astigmatism correction with toric lens or corneal incisions. If it is determined that the measurements are not consistent then subject will be excluded from the study.

The surgeon's standard pre cataract surgery treatment will be used in all his patients.

2. Visit 2: The surgeon may use his preferred cataract extraction technique (manual or laser) for eyes randomized to Group A. Eyes randomized to Group B will undergo laser assisted phacoemulsification (primary incision, capsulorhexis and lens fragmentation) using the surgeon's preferred laser settings. The secondary incision will be made with the laser or manually, at the surgeon's discretion. The lens will be implanted in the bag. The surgeon's standard post cataract surgery treatment will be used in all his patients.
3. Visit 3: Assessment will include uncorrected ETDRS visual acuity, intraocular pressure, slit lamp examination, corneal incision location and/or toric IOL orientation.
4. Visit 4 and 5: Assessment will include uncorrected and best-corrected ETDRS visual acuity (UCVA / BCVA), manifest refraction, auto refractor keratometry, Lenstar, VERION™ Reference Unit, corneal topography, intraocular pressure, and slit lamp examination. The location of all corneal incisions as well as toric IOL orientation will be documented.

Adverse events and device deficiencies/quality complaints will be monitored and recorded at all study visits.

**Table 1.** Visits and Study Assessments

Study Assessments	Visit 1 Preoperative	Visit 2 Operative	Visit 3 Day 1	Visit 4 Day 20-40	Visit 5 Day 75-105
Inclusion/Exclusion Criteria	x				
Consent Subject	x				
Patient demographics (age, gender, race, ethnicity)	x				
Manifest Refraction	x			x	x
UCDVA	x		x	x	x
BCDVA	x			x	x
Tonometry (IOP)	x		x	x	x
Complete slit lamp exam	x		x	x	x
Dilated fundus exam	x			†	†
Auto refractor keratometry	x			x	x
Atlas corneal topography	x			x	x
Lenstar LS900 measurements	x			x	x
Verion™ Reference Unit measurements	x			x	x
Verion™ Planner	x				
Alcon Toric calculator	x				
LRI calculator	x				
Incision Size and Location		x			
Record Lens Model Implanted (Attach label, or record manufacturer, model, power)		x			

VerifEye or VerifEye + information		x			
Post-IOL implantation incision size		x			
LenSx parameters		x			
Corneal arcs/toric IOL orientation		x	x	x	x
Adverse events / device deficiency	x	x	x	x	x

x To be performed as scheduled

† To be performed as deemed necessary by the investigator.

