### **STUDY DESIGN AND METHODS:**

1. **Test article:** The VERION™ Image Guided System: Digital Surgical Planning and Positioning Tools + ORA System with VerifEye or VerifEye +.
2. **Study Design:** Prospective, randomized, contralateral eye study.
3. **Subjects:**
  - a. **Inclusion Criteria:**  
Subjects MUST fulfill the following conditions to qualify for enrollment into the trial
    1. Subject is undergoing bilateral cataract extraction or refractive lens exchange with intraocular lens implantation and astigmatism correction.
    2. Gender: Males and Females.
    3. Age: 50 years and older.
    4. Willing and able to provide written informed consent for participation in the study
    5. Willing and able to comply with scheduled visits and other study procedures.

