## 5. Study Surgery Procedures

Eyes of the study participants will be randomly assigned to one of two groups:

- a. Group A, surgeon standard of care prior to getting VERION™ Image Guided System. Spherical power will be selected using the surgeon's preferred formula (Haigis, Holladay 2, Holladay, or other) and biometry method (IOL Master, Lenstar). Astigmatism correction will be planned using the surgeon's preferred keratometry method and calculator/nomogram to determine toric power and corneal incisions (i.e. Alcon toric calculator, Holladay toric calculator, AMO LRI calculator, etc). At time of surgery, axis of placement will be marked using blue ink marks. Corneal incisions will be made manually.
- b. Group B, VERION™ Image Guided System: Digital Surgical Planning and Positioning Tools + ORA System with VerifEye or VerifEye +. Spherical power of the IOL will be selected using the Verion™ Planner with the surgeon's preferred formula with an optimized A-constant (Haigis, Holladay 2, Holladay, or other). Both toric lenses and corneal incisions will be calculated with the Verion™ Planner using the Verion™ Reference Unit keratometry and white to white measurements, and Lenstar biometry. The VERION™ Digital Markers L and M will be used for axis of placement and confirmed using ORA System with VerifEye or VerifEye +.

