## 6. Study Visit Schedule and Assessments (Table 1).

- a. **Visit Schedule:** Patients will be examined at the following intervals:

1. Visit 1: Screening and enrollment: Preoperative evaluation completed not more than eight weeks before surgery

2. Visit 2: Day of Surgery
3. Visit 3: Day 1 (12 to 48 hrs) after surgery
3. Visit 4: Month 1:  $30 \pm 10$  days postoperative after second eye surgery
4. Visit 5: Month 3:  $90 \pm 15$  days postoperative after second eye surgery

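### The allocation follows whichever eye is operated first, and the protocol does not require that eye to be named before the allocation is known or bind the allocation to it

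*Combined protocol and SAP*

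**What the plan says.** The design is described as "Prospective, randomized, contralateral eye study" (Study Design and Methods, item 2).

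The allocation rule is in section 6.b, under Visit 1: "The first eye undergoing surgery will be randomized to either one of the two groups". Then: "The fellow eye will be assigned to the alternate group". One random draw therefore settles both eyes of a patient.

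On timing, the same section says: "Eyes will be randomized after all calculations have been completed". By then each eye has its keratometry, biometry, topography and VERION measurements, and it has two treatment plans: "Both IOL power and astigmatism correction will be calculated using the surgeon's current standard of care as well as using the VERION™ Image Guided System". Consistency of the measurements and eligibility for astigmatism correction are also reviewed before randomization.

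The group is plain to the operating surgeon. Section 5 says for Group A: "At time of surgery, axis of placement will be marked using blue ink marks. Corneal incisions will be made manually". For Group B it says: "The VERION™ Digital Markers L and M will be used for axis of placement and confirmed using ORA System with VerifEye or VerifEye". Section 6.b also makes laser-assisted surgery compulsory in Group B and leaves the technique to the surgeon in Group A.

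No section says who decides which eye goes first, by what rule or when, whether the decision is written down before the allocation is seen, or what happens to the allocation if the order changes. I looked in Study Enrollment Procedures, Study Surgery Procedures, the visit schedule and Table 1, the completion criteria, Sample Size and Statistical Considerations. Allocation concealment and masking are not described either.

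**The concern.** In a contralateral trial the comparison is fair because chance alone decides which of a patient's two eyes goes to which group. Here chance decides the group of a place in the surgical order, and the order decides which eye holds that place. If the order is settled before the draw, the two amount to the same thing. If it can still move afterwards, whoever sets the order also sets the assignment of eyes, with the measurements and both plans for each eye available.

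The primary endpoint, residual refractive cylinder at 3 months, plausibly depends on features known for each eye before surgery, such as the amount of corneal astigmatism. If the more favorable eye tended to go to one group, the difference between groups would contain a component unrelated to the devices. The type I error would then exceed the stated 5%.

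**Working it through.** **Step 1: is the route open on the text?** Four statements, taken together, decide this.

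- The draw attaches to the first eye operated (6.b, Visit 1).
- The draw follows all measurements and both sets of calculations (6.b, Visit 1).
- The surgeon must know the group in order to operate (section 5; 6.b, Visit 2).
- No section fixes the order before the draw or ties the group to a named eye.

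Suppose the draw gives first eye = B. If the right eye goes first, right = B and left = A. If the order is then reversed, left = B and right = A, and the protocol's rule has still been followed. The route is open.

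**Step 2: how large could the effect be?** The plan gives no figure for this, so what follows is an illustration.

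Inputs from the plan:
- SD of 0.35 D and relevant difference of 0.25 D (Sample Size)
- two-sided 5% level (Statistical Considerations)

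As a check on these inputs, a two-sample t-test at 80% power needs 31.8, so 32, eyes per group, close to the stated 34. The present point does not depend on that figure.

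Assumptions not in the documents:
- between-eye correlation of 0.5, for both the outcome and the prognostic part
- preoperative features explain a share R² of the variance in residual cylinder, with R² from 0.1 to 0.3
- in a fraction f of pairs the order is chosen by prognosis, always favoring the same group; the remaining pairs are random
- no true difference between groups, and a paired t-test

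The Sample Size section gives 40 eyes (20 subjects) per group, so both 20 and 40 pairs are shown.

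Formulas:
- SD of the prognostic difference between eyes = 0.35 × √R² × √(2 × (1 − 0.5)) = 0.35 × √R²
- mean absolute prognostic difference = that SD × √(2/π)
- bias = f × mean absolute prognostic difference
- SD of the paired outcome difference = 0.35 × √(2 × (1 − 0.5)) = 0.35 D
- type I error = two-sided rejection probability from the noncentral t with noncentrality bias × √N / 0.35

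Worked case, R² = 0.2: SD = 0.35 × 0.447 = 0.157 D. Mean absolute difference = 0.157 × 0.798 = 0.125 D. Bias = 0.25 × 0.125 = 0.031 D at f = 25%, and 0.5 × 0.125 = 0.062 D at f = 50%. These are 12% and 25% of 0.25 D.

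| R² | f | Bias (D) | Type I error, 20 pairs | Type I error, 40 pairs |
|---|---|---|---|---|
| 0.1 | 5% | 0.004 | 5.0% | 5.1% |
| 0.1 | 10% | 0.009 | 5.1% | 5.3% |
| 0.1 | 25% | 0.022 | 5.8% | 6.8% |
| 0.1 | 50% | 0.044 | 8.4% | 12.2% |
| 0.2 | 25% | 0.031 | 6.7% | 8.5% |
| 0.2 | 50% | 0.062 | 11.8% | 19.6% |
| 0.3 | 5% | 0.008 | 5.1% | 5.2% |
| 0.3 | 10% | 0.015 | 5.4% | 5.8% |
| 0.3 | 25% | 0.038 | 7.5% | 10.4% |
| 0.3 | 50% | 0.077 | 15.3% | 27.1% |

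**Step 3: cross-check by simulation.** This used 20,000 trials per setting with no true effect. The prognostic factor had correlation 0.5 with the outcome (R² = 0.25), and the favorable eye went to Group B with probability 0.75, which corresponds to f = 2 × 0.75 − 1 = 50%. The false difference was about 0.07 D and the type I error 0.14 with 20 pairs and 0.25 with 40. Both lie between the table's R² = 0.2 and 0.3 rows. With no steering the error stayed at about 0.05.

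**The case against.** The strongest reply is that the protocol is silent on the order and does not say it is left open. The allocation sentence can be read as describing an eye already identified when it is randomized, and section 5 also speaks of eyes being randomly assigned. Randomizing the first eye is a legitimate design, so the lack of a right/left label is no flaw in itself. All of that stands. What remains is that nothing makes the harmless reading the required one.

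A reader might infer that the surgeon does choose which eye goes to which group. The documents do not support that. They show that such a choice would be possible and say nothing about whether it is made. Bias also needs a choice related to prognosis and in a consistent direction. A change of order made purely for scheduling, unrelated to prognosis, would not produce it.

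A reader might also infer a gap of up to eight weeks in which the order could be changed. The visit schedule says "Preoperative evaluation completed not more than eight weeks before surgery". That limits the age of the evaluation. It does not say when the allocation is opened, and Table 1 has no row for randomization.

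Finally, one might say that selection would leave no trace. That is too strong. Refraction, keratometry and topography are recorded before surgery, so gross steering on measured astigmatism could be seen in a baseline comparison by group. The plan specifies no such comparison, and it would not reveal selection on unmeasured features.

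The size is fairly challenged too: it depends on the assumed steering fraction and is negligible at 5-10%.

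**Conclusion.** The point holds as a gap in the allocation rule. The protocol does not require the first eye to be named before the allocation is known and does not keep the allocation with that eye if the order changes. The documents give no evidence that selection occurs. The absence of masking for the surgeon is an inference from the procedures, since the documents make no statement on masking.

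The possible harm runs from negligible at 5-10% steering to a bias of almost a third of the relevant difference at the top of the range (0.077 / 0.25 = 31%). Only the SD, the relevant difference and the significance level come from the plan. The correlation, the variance explained, the steering fraction and its constant direction are assumed. The change is worth making because it closes a route to bias in the primary comparison at almost no cost, whatever the true size.

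**What to change.** In section 6.b, Visit 1, add a rule to this effect: before the allocation is opened, the eye to be operated first (right or left), chosen by the practice's usual rule, is recorded on the randomization form; the allocation applies to that named eye even if the order later changes; and eyes are analysed by that allocation. Randomizing the right eye directly to Group A or B, with the left eye taking the other group, would work equally well.

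The cost is one protocol sentence and one line on the form. The sample size does not change. The small downside is that a later change of order no longer changes an eye's group, so both procedures must be available in whichever order the eyes are operated.

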#### **STATISTICAL CONSIDERATIONS**

All data will be collected by the research team. Data will be entered into a database. The database will be password protected and access will be restricted to study personnel. Data analysis will be performed without patient identification. Statistical analysis will be done using standard descriptive statistics and other tests as deemed appropriate based on the characteristics of the data to be analyzed. Secondary endpoints will be analyzed only if the primary endpoint demonstrates a statistically significant difference between groups. Corneal and refractive astigmatism are likely to be correlated. A Bonferroni correction will be applied where indicated for evaluating significance. Mean spherical equivalent refraction is not expected to be highly correlated to the measured astigmatism, nor is mean keratometry, so multiplicity considerations will not be required for these variables. All statistical tests will be two-sided and interpreted at a 5% significance level. Comparisons between the two groups will be made. Data analysis will be conducted by a third party consultant.

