**Primary Endpoint:**

- Residual refractive cylinder at 3 months

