**Secondary Endpoints:**

- Residual mean spherical equivalent refraction at 3 months
- Residual corneal astigmatism at 1 month and 3 months
- Residual refractive sphere at 1 month and 3 months
- Interim refractive cylinder at 1 month
- Percentage of eyes with postoperative MRSE accuracy to target  $\leq 0.5D$  at 1 and 3 months
- Uncorrected and best-corrected visual acuity at 1 month and 3 months
- Axis of placement (actual vs. intended)
- Lenstar K's vs. Verion K's
- Corneal incisions stability (manual vs. laser arcs) at 3 months after surgery - based on manifest cylinder and keratometry measurements from 1 and 3 months, noted above.

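### The primary endpoint evidently rests on manifest refraction, yet the plan specifies neither masking of the refracting examiner nor an order of assessments that would protect it

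*Combined protocol and SAP*

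**What the plan says.** The Primary Endpoint section gives one line: "Residual refractive cylinder at 3 months". It names no measurement method. The assessments for Visits 4 and 5 in section 6.b include "manifest refraction, auto refractor keratometry, Lenstar", and manifest refraction is the only item in that list that is expressly a refraction. The last item under Secondary Endpoints describes incision stability as "based on manifest cylinder and keratometry measurements from 1 and 3 months", which supports reading the refractive cylinder as a manifest one.

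Section 2 describes the design as "Prospective, randomized, contralateral eye study", without a masking term. The first operated eye is randomized, and "The fellow eye will be assigned to the alternate group".

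Slit lamp examination takes place at the same two visits, and section 6.b adds: "The location of all corneal incisions as well as toric IOL orientation will be documented". Nothing states which assessment comes first or who performs each one.

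Statistical Considerations says "All data will be collected by the research team", that the analysis is done without patient identification, and that "Data analysis will be conducted by a third party consultant".

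**The concern.** Manifest refraction is reached through the examiner's choices and the subject's answers, so expectation can influence it. The background section states the expectation: refractive results should be better with VERION plus ORA. Each subject contributes one eye to each group and both are examined at the same visit. An examiner who knew the assignment could therefore shift the very contrast that is analysed.

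The same visits offer a route to that knowledge. Group A corneal incisions are manual (section 5), and the secondary endpoints contrast manual with laser arcs, so in eyes with arcs the slit lamp may disclose the group. Anonymous analysis by an outside consultant comes too late to help, because it cannot remove a bias already in the recorded refraction.

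The difference the trial is sized for is only 0.25 D, so a modest average shift matters. Secondary endpoints are tested only if the primary is significant, so a falsely positive primary would also open that gate.

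**Working it through.** **Inputs from the Sample Size and Statistical Considerations sections.** SD about 0.35 D; relevant difference 0.25 D; two-sided 5% level; power 0.8; 34 eyes per group before inflation and 40 after.

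**The plan's own figure.** An exact two-sample t-test with these inputs needs 32 eyes per group (power 0.803), and 34 gives power 0.827, so 34 is reproduced to within 2 eyes. Inflation by 20% gives 34 × 1.2 = 40.8, against the stated 40. Masking does not change this number. The calculation below concerns the type I error only.

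**Number of pairs.** The final size is given as 40 eyes and, in parentheses, 20 subjects per group. With one eye per group from each subject, that can mean 20 or 40 pairs, so both are shown.

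**Assumptions not in the documents.** Refraction recorded in 0.25 D steps, and one step in favour of Group B in a share of that group's eyes:
- 20% of eyes: 0.20 × 0.25 = 0.05 D average bias, or 0.05/0.25 = 20% of the target difference.
- 40% of eyes: 0.40 × 0.25 = 0.10 D, or 40% of the target difference.

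The between-eye correlation ρ is taken as 0 to 0.5.

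**Paired t-test, no true effect.** The SD of the within-subject difference is 0.35 × √(2(1 − ρ)): 0.495 D at ρ = 0, 0.414 D at 0.3 and 0.350 D at 0.5. The noncentrality is bias × √n / SD of the difference. For example, with n = 40, bias 0.10 D and ρ = 0.5 it is 0.10 × 6.325/0.350 = 1.807. Against a critical value of 2.023 on 39 degrees of freedom, the rejection probability is 42.2%.

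| Bias | Pairs | ρ = 0 | ρ = 0.3 | ρ = 0.5 |
|---|---|---|---|---|
| 0.05 D | 20 | 7.1% | 8.1% | 9.3% |
| 0.05 D | 40 | 9.6% | 11.6% | 14.3% |
| 0.10 D | 20 | 13.8% | 17.7% | 22.9% |
| 0.10 D | 40 | 23.8% | 31.9% | 42.2% |

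The rate rises with the number of pairs, so a larger trial would not cure the problem.

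**Unpaired t-test, ρ = 0.3.** The plan presumes a t-test between groups without saying that it is paired, and leaves the final choice of test open. Simulation (400,000 trials per setting) gives 3.9% with 20 pairs and 5.9% with 40 at 0.05 D, and 10.2% and 20.4% at 0.10 D. These rates are lower because an unpaired test ignores a positive correlation. Its statistic then has SD of about √(1 − 0.3) = 0.837, so with no bias at all it rejects only about 2% of the time (1.96/0.837 = 2.34, two-sided tail 1.9%). Relative to that baseline, 0.05 D still doubles or triples the rate, although the absolute figure stays near the nominal 5%.

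**The case against.** **Silence is not a statement that examiners are unmasked.** A reader might infer that the refracting staff know each eye's group. The documents do not say so. They do not identify who refracts or what that person is told. What stands is that masking is not specified.

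**The slit lamp does not always give the group away.** Extraction in Group A may be manual or laser, and toric lenses are used in both groups, so neither laser signs nor lens orientation alone identifies the assignment. Disclosure is most plausible in eyes with arcs, and the plan does not give the split between arcs and toric lenses. This objection stands, so the claim is limited to possible disclosure.

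**Refraction is already listed before the slit lamp.** That is true of the list for Visits 4 and 5, but a list does not mandate a sequence. Incision and axis findings are also documented at Visit 3, so an examiner may already know the group by Visit 4.

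**Instrument-based measures exist.** Lenstar, VERION keratometry and topography are repeated at both visits, and residual corneal astigmatism is a secondary endpoint, so a positive primary would face an instrument-based comparison. This helps only partly: in an eye with a toric lens, corneal astigmatism is not the residual refractive cylinder. A reader might also infer that an objective refractive cylinder is already collected. The plan lists only auto refractor keratometry and names no autorefraction cylinder as a recorded outcome.

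**The size is driven by assumptions.** This is correct. The step size, the share of eyes shifted, the single direction of the shift and the correlation are all assumed, and with an unpaired test the 0.05 D scenario leaves the absolute rate close to 5%.

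**Conclusion.** The point holds as a gap in protection against bias. The primary endpoint evidently depends on a subjective refraction, the design sets the two groups against each other within each subject, and the plan specifies neither masking of the examiner nor a sequence of assessments. Nothing downstream in the analysis can repair this.

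The documents do not show that bias will occur. If it did, with 20 to 40 pairs the false-positive rate would be about 7% to 14% (paired) or 4% to 6% (unpaired, ρ = 0.3) for a 0.05 D bias, and about 14% to 42% or 10% to 20% for 0.10 D. These ranges rest on an assumed bias and correlation and on SD 0.35 D. The change should be made because it is cheap relative to what it protects.

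**What to change.** In section 6.b:
- Name manifest refraction as the source of the primary endpoint.
- State that the person who performs it at Visits 4 and 5 is not told the eye's allocation and has no access to operative records.
- Require refraction and visual acuity to be completed before slit lamp examination and incision or axis documentation. Where possible, use an existing staff member who did not do those tasks for that subject at earlier visits.
- Ask subjects not to disclose which eye had which system.
- If the autorefractor already outputs refractive cylinder, record it at the same visits and prespecify it as a supportive analysis.

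The cost is protocol wording, a small workflow constraint at two visits and possibly one added data field. Staffing is not described, so a reader should not infer that a separate examiner is available for every subject; refracting first without access to operative records helps even when one person does everything. Masking would be partial in any case, because knowledge from earlier visits and the subject's own expectation may remain. The report should say so.
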